10.6.1. Demographics and Baseline Characteristics

Demographics (age, race, sex), baseline characteristics (e.g., height, weight), and subject disease characteristics will be summarized for all enrolled subjects.

Descriptive statistics will be calculated for continuous variables (age and weight) and frequency counts and percentages will be tabulated for categorical variables (e.g., gender, race, and body mass index).

10.6.2. Efficacy Analyses

Hemoglobin results obtained from the central laboratory will be used for all efficacy analyses.

Baseline Hb value for efficacy analysis is defined as the mean of the central laboratory Hb value from the Baseline Visit Day 1 (prior to receiving the first dose of study drug in this study), plus any other central laboratory Hb values obtained within 15 days prior to Day 1. Baseline eGFR, ferritin, TSAT, and other efficacy endpoints are defined as the last value prior to the first dose of study treatment.

All efficacy analyses will be based on the EE population.

- Monthly mean Hb values and changes from baseline will be summarized descriptively for the Dialysis, Non-Dialysis, and Newly Initiated populations at each scheduled time point as well as monthly
- The number (%) of subjects maintaining Hb ≥ 10 g/dL during study participation, the composite rate of summarized rescue therapy events (transfusions, IV iron, ESAs) and rate of individual rescue therapy events, and the number (%) of subjects receiving phlebotomies will be summarized for the Dialysis, Non Dialysis and Newly Initiated populations
- The dose level at the time of Hb response will be summarized descriptively
- The frequency of dose increases and decreases and use of rescue therapy will also be tabulated. Median time to Hb response will be estimated for each subject previously receiving placebo (Newly Initiated group) using the Kaplan-Meier method. Hemoglobin response is defined as a Hb increase from baseline of at least 1.0 g/dL. In addition, median initial responsive time and dose will be tabulated to evaluate when an initial Hb change from baseline reaches at least 1.0 g/dL. Number (%) of

subjects, scheduled Hb values, and consecutive Hb values achieved for a variety of Hb ranges between 11.0 and 13.0 g/dL, as well as above or below these ranges, during 4-week study intervals throughout the treatment period will be tabulated.

10.6.3. Exploratory Analyses

Quality of life composite scores, as well as selected subscale scores will be compared to baseline values and between treatment assignments.

Descriptive statistics will be generated for exploratory endpoints and biomarkers. Correlations between parameters will be explored.

10.6.4. Safety Analyses

All subjects who received any dose of roxadustat will be included in the safety analyses.

All safety assessment data, including laboratory assessments, vital signs, physical examinations, ECGs, AEs, and concomitant medications and therapies, will be summarized by time point of collection as appropriate for the Dialysis, Non-Dialysis, and Newly Initiated populations.

An AE data listing by subject, including verbatim term, preferred term, study treatment, severity, and relationship to study treatment, will be presented.

The number (%) of subjects experiencing treatment-emergent AEs will be summarized using frequency counts for the Dialysis, Non-Dialysis, and newly initiated populations.

Descriptive statistics will be calculated for quantitative safety data and frequency counts will be compiled for classification of qualitative safety data. Laboratory data will be summarized for each time point that specimens are collected. Change-from-baseline values may be calculated for selected laboratory parameters (baseline refers to blood drawn prior to the first study treatment). Laboratory values outside of normal limits will be identified in the subject data listings with flags for high and low values. Laboratory results obtained from the central laboratory will be used for all safety analyses.

ECG results will be classified using frequency counts for normal, clinically insignificant abnormalities, and clinically significant abnormalities by time point of collection. Descriptive statistics will be calculated for QT intervals.

Blood pressure, HR, and respiratory rate data will be summarized descriptively by various time intervals both as absolute values and as changes from baseline.

A summary table and/or listing will present all abnormal physical examination results throughout the study.

10.7. Statistical Analysis Plan

A detailed Statistical Analysis Plan (SAP) will be finalized prior to data analysis. Any significant changes to the analyses described in this protocol will be highlighted in the SAP. Deviations in analyses from the SAP will be detailed in the clinical study report.

11. SAFETY

11.1. Background

Adverse event reports from investigators are the critical building blocks to the developing safety profile of the study drug. Therefore, with the exception of study endpoints, the investigator must immediately report to the sponsor all SAEs, regardless of whether the investigator believes they are drug related. Additionally, the investigator must record nonserious AEs at regular intervals during the course of the study.

The definitions of an AE, suspected adverse reaction, adverse reaction, and SAE are described below in accordance with the Food and Drug Administration (FDA) Final Rule Vol 75, No 188, September 29, 2010 and the International Conference on Harmonization (ICH) E2A guidance.

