3. ENDPOINTS AND ASSESSMENTS

3.1. Efficacy

The efficacy endpoints in this study are:

- Mean monthly Hb values over time;
- Number (%) of subjects maintaining monthly (monthly defined as a 4-week interval) mean Hb at ≥ 10 g/dL during study participation upon correction (correction is defined as having achieved 2 consecutive Hb values of ≥ 10 g/dL);
- Number (%) of subjects maintaining Hb between 10-13 g/dL for at least 60% of scheduled Hb assessments after the first Hb value is 10 g/dL or higher.
- Composite rate of summarized rescue therapy events (transfusions, IV iron, ESAs) and rate of individual rescue therapy events;
- Number (%) of subjects with phlebotomies;
- Roxadustat weekly total doses over time;
- Dose adjustment frequencies;
- Hb variability;
- Number (%) of subjects withdrawn from the study due to inadequate efficacy.

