11.3. Procedures for Eliciting, Recording, and Reporting Adverse Events

11.3.1. Adverse Event Reporting Period

The study period during which all AEs and SAEs must be reported begins after informed consent is obtained and ends 28 days after the last treatment.

Adverse events will be followed until resolved, stable, or until the subject's last study visit. If an AE is not resolved or stabilized at the subject's last visit, it is up to the discretion of the investigator and study medical monitor to determine if further monitoring of the event is warranted.

Adverse events collected prior to dosing of study drug will be considered "treatment non-emergent" while those reported after the first dose of study drug will be considered "treatment emergent" and be assessed for relationship to study drug.

During the AE reporting period, study site personnel will query each subject at each visit to actively solicit any AE occurring since the previous visit. This does not preclude the site from collecting and recording any AEs reported by the subject to site personnel at any other time.

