11.3.3. Assessing Relationship of Adverse Event to Study Drug

Most of the information about the safety of a drug prior to marketing comes from clinical trials; therefore, AE reports from investigators are critically important. Moreover, appropriately deciding whether the AE meets the definition of a suspected adverse reaction is usually the most difficult determination, but it is critical to avoid the miscategorization of the product's safety profile.

Due to the historical tendency for assessment of relationship to default as possibly related, the FDA has issued new guidance that clarifies the intent of the phrase "reasonable possibility" in the definition of "associated with the use of the drug." Default reporting of individual events as "possibly related" is uninformative and does not meaningfully contribute to the development of the product safety profile.

The investigator must provide an assessment of the relationship of the AE to study drug in accordance with the guidance below. Absence of an alternative cause would not normally be considered enough evidence to assess an event as "possibly related" or "related" to study drug.

Related (Adverse Reaction):

- Any event for which there is evidence to conclude that the study drug caused the event.

Possibly Related (Suspected Adverse Reaction):

- A single occurrence of an event that is uncommon and known to be strongly associated with drug exposure, such as angioedema, anaphylaxis during infusion, rhabdomyolysis, Stevens-Johnson syndrome, etc.
- One or more occurrences of an event that is not commonly associated with drug exposure but is otherwise uncommon in the population exposed to the drug, such as tendon rupture.

Not Related:

- The event represents the underlying disease (e.g., disease-related symptoms, disease progression)

- The event represents a comorbid condition present at the time the subject entered the study
- The event represents a known adverse reaction associated with a co-medication received by the study subject
- The event is common for the study population (e.g. cardiovascular events in an elderly population)
- The event has no plausible relationship to study drug
- The event is a study endpoint (e.g., mortality, major morbidity)

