11.3.4. Reporting Serious Adverse Events on the SAE Report Form

All SAEs must be reported to FibroGen immediately.

To report an SAE, the investigator must e-mail or fax an SAE Report Form to FibroGen within 24 hours of becoming aware of the event. Follow-up reports must be submitted in a timely fashion as additional information becomes available.

For each SAE observed, the investigator should obtain all of the information available about the event, including (but not limited to): hospital discharge diagnoses, hospital discharge note, death certificate, appropriate laboratory findings (including autopsies and biopsy results), and clinical examinations (including radiological examinations and clinical consultations).

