11.3.4.2. Deaths

For any death occurring during the subject's study participation, regardless of attribution, the investigator will report the death immediately to the study medical monitor.

The investigator should notify FibroGen of any death or other SAE occurring after a subject has discontinued or terminated study participation that may reasonably be related to the study.

The investigator must submit the SAE Report Form and complete the appropriate CRF page for the event that led to the subject's death. This includes death attributed to progression of anemia or CKD.

When reporting a death, the event or condition that caused or contributed to the fatal outcome should be recorded as the primary event term on the SAE Report Form.

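### Protocol 11.1 exempts undefined study endpoints from immediate SAE reporting, against 11.3.1 and 11.3.4, and 11.3.3 lets endpoint status decide that an event is Not Related

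*Protocol*

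**What the plan says.** **Reporting.** Protocol 11.1 states that "with the exception of study endpoints, the investigator must immediately report to the sponsor all SAEs", whether or not the investigator thinks the drug was responsible. Section 11.3.4 states "All SAEs must be reported to FibroGen immediately" and sets a 24-hour limit for the report form. Section 11.3.1 defines the period in which "all AEs and SAEs must be reported begins after informed consent is obtained and ends 28 days after the last treatment". Neither of the last two carries an exception. For deaths during participation, 11.3.4.2 says that "regardless of attribution, the investigator will report the death immediately to the study medical monitor". It also requires an SAE form and adds: "This includes death attributed to progression of anemia or CKD".

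**Causality.** Section 11.3.3 gives the investigator a list of grounds for calling an event Not Related. One of them reads "The event is a study endpoint (e.g., mortality, major morbidity". The same section makes the sponsor responsible for the final causality judgement, and says that in most cases it will rest on pooled data.

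**Endpoints.** Section 3.1 lists haemoglobin measures, phlebotomy, dose and dose-adjustment measures, withdrawal for inadequate efficacy, and rescue: "Composite rate of summarized rescue therapy events (transfusions, IV iron, ESAs) and rate of individual rescue therapy events". It lists neither mortality nor major morbidity. Section 3.2, under the same chapter title of endpoints and assessments, lists AEs and SAEs as safety measures.

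**Use in the analysis.** Protocol 10.6.4 plans an AE listing that shows relationship for each event. SAP 11.1 plans a TEAE table by relationship (item 3), along with tables and an SAE listing that do not depend on relationship (items 1, 4 and 6).

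**The concern.** There are two faults, and each stands without the other.

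The first is a contradiction about what must be reported at once. An investigator who relies on 11.1 may hold back a serious event that 11.3.4 requires within 24 hours, and the exception does not say which events it means.

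The second is a causality rule that does not depend on the facts of the case. Whether a trial has chosen to count an event as an endpoint says nothing about whether the drug caused it. Long-term safety is part of the primary objective (Section 2.1), there is no control group (Section 4.1.1), and 15 subjects entered (SAP Section 3). With no concurrent comparison inside the study, the case-level relationship call is one of the few causal signals it produces, so that call should rest on clinical evidence.

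**Working it through.** The protocol gives no figure on this point and no arithmetic applies. The check sets the sections side by side.

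**Step 1: do the reporting rules agree?**
- 11.1: all SAEs at once, except study endpoints.
- 11.3.1: all AEs and SAEs from consent to 28 days after the last treatment; no exception.
- 11.3.4: all SAEs at once, form within 24 hours; no exception.
- 11.3.4.2: every death during participation at once, whatever the attribution, with an SAE form.

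They do not agree, and no section says which prevails.

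**Step 2: what could the exception cover?** Three readings are open.
- *Endpoints in Section 3.1.* The possible overlap with SAEs is rescue, for example a hospital admission that leads to transfusion. The admission is serious under 11.2.4 and the transfusion counts toward the rescue endpoint. No section says whether the admission is then itself an endpoint.
- *The examples in 11.3.3.* Mortality falls under 11.3.4.2 and is reported anyway. Non-fatal major morbidity has no such protection.
- *Section 3.2.* If AEs and SAEs count as endpoints, the exception cancels the rule.

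On every reading, the events left in conflict are non-fatal. The protocol's other exemption is better drafted: 11.2.1 and 11.3.6 excuse out-of-range haemoglobin values from AE reporting, name the data, and say where they will be analysed. The endpoint exception does neither.

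**Step 3: does the Not Related bullet have an object?** Its examples, mortality and major morbidity, are absent from Section 3.1. Either the bullet applies to nothing it names, or an investigator follows the examples and treats deaths and major morbidity as endpoints. The reporting rule in 11.3.4.2 does not settle this, because it governs whether a death is reported and not how it is classified.

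**Step 4: does the call reach the analysis?**
- Protocol 10.6.4 lists relationship by event, and SAP 11.1 item 3 tabulates it.
- SAP 13.5 sets a missing relationship to Related. An event actively marked Not Related is not missing, so this gives no protection.
- SAP 11.1 counts the most related occurrence of a preferred term within a subject. This helps only if the same subject has another occurrence of that term with a stronger relationship.
- Protocol 11.3.3 gives the sponsor the final assessment, but the SAP does not say whether the investigator's or the sponsor's call is tabulated.

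The investigator's call can therefore pass unchanged into the listing and the table.

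**The case against.** The case for leaving the text alone has substance.

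- *Section 11.1 is background and 11.3.4 is the operative rule.* Most sites would probably follow 11.3.4. But 11.1 is worded as an obligation, and nothing ranks one section above the other.
- *Deaths.* A reader might infer that death reports could be delayed. The documents do not support that: 11.3.4.2 requires immediate reporting of every death during participation.
- *Mortality is not an endpoint here, so the bullet is idle.* This is right on a strict reading. A reader might infer the opposite extreme, that all deaths and major morbidity would be recorded as Not Related. That requires every investigator to treat as an endpoint something Section 3.1 does not list, and nothing in the documents shows it. What stands is that the bullet's own examples invite the error.
- *The sponsor decides in the end.* This reduces the effect of a wrong investigator call. It does not remove it, because the tabulated source is unnamed and a review of this study's data alone has no concurrent control.
- *The key safety tables ignore relationship.* This stands in full. TEAEs by system organ class and preferred term, treatment-emergent SAEs and the SAE listing are already planned. Counts of reported events do not change with the relationship call, and no further statement that all-causality results should lead is needed.
- *Another bullet would often give the same answer.* Section 11.3.3 also lists "The event is common for the study population (e.g. cardiovascular events in an elderly population" as Not Related, so some events would stay in that category after the endpoint bullet is removed. That limits the effect of the change but does not justify the bullet.

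**Conclusion.** The concern holds in a limited form. The reporting rule in 11.1 contradicts 11.3.1 and 11.3.4 for non-fatal serious events that someone regards as endpoints. The endpoint bullet in 11.3.3 assigns causality on a ground that has no bearing on causality, and it can bias the AE listing and the TEAE-by-relationship table toward Not Related. It does not affect the all-causality tables.

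The size cannot be computed from the documents. A reader might try to express it as the share of one subject among 15, but any single reclassification would carry that weight whatever its cause, so it does not measure this fault. The documents do not show that any report was late or any event misclassified.

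The conclusion assumes that at least some investigators would act on 11.1 or on the examples in 11.3.3 as written, and that the investigator's assessment may be what is tabulated. If the sponsor's assessment is tabulated and was made without regard to endpoint status, the effect on the table disappears and only the reporting conflict and the investigator-level rule remain.

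**What to change.** **Protocol.**
1. In 11.1, delete the opening clause that excepts study endpoints, so that the section agrees with 11.3.1, 11.3.4 and 11.3.4.2.
2. In 11.3.3, delete the study-endpoint bullet from the Not Related list. The remaining bullets already cover underlying disease, comorbidity, co-medication, common events and implausibility.

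**SAP.** Section 3 describes enrolment as past, so protocol edits may not change calls already recorded. Therefore:

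3. In 11.1, state whether the investigator's or the sponsor's relationship assessment is tabulated.
4. Flag any serious event that was called Not Related on the ground of endpoint status. The documents do not say whether the reason for a call is recorded, so this may need site queries.

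**Cost.** A small protocol amendment, which under Section 13.2 needs IRB/IEC approval before it takes effect; two short SAP additions; a review of serious events from 15 subjects; and possibly a few more SAE reports from investigators to the sponsor. No treatment or visit rule changes.

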11.2. Definitions

11.2.1. Definition of an Adverse Event

An AE is any untoward medical occurrence associated with the use of a drug in humans, whether or not considered drug related.

An AE can be any unfavorable and unintended sign (e.g., an abnormal laboratory finding), symptom, or disease temporally associated with the use of a drug, without any judgment about causality. An AE can arise from any use of the drug (e.g., off-label use, use in combination with another drug) and from any route of administration, formulation, or dose, including an overdose.

Out-of-range Hb values need not be reported as AEs as these Hb values will be captured and analyzed in the efficacy analyses.

An AE includes medical conditions, signs, and symptoms not previously observed in the subject that emerge during the protocol-specified AE reporting period, including signs or symptoms associated with an underlying condition that were not present prior to the AE reporting period (see [Section 11.3.1](#)).

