11.3.6. Abnormal Laboratory Findings

Laboratory values will be collected throughout the study to assess for safety. The investigator must review and assess all laboratory results in a timely manner and must report abnormal laboratory findings if they are clinically significant or if there are associated signs and symptoms.

An abnormal laboratory finding in absence of any other signs or symptoms is not necessarily an AE/SAE. If the abnormal laboratory finding is accompanied by signs or symptoms, report the signs and symptoms as the AE/SAE in lieu of the abnormal laboratory value. If a diagnosis is available, report the diagnosis.

Clinically significant laboratory abnormalities that reflect a change from the initial screening value and that require active management may be considered AEs (e.g., abnormalities that require study treatment dose modification, discontinuation, more frequent follow-up assessments, etc.). However, out-of-range Hb values should not be reported as AEs as these Hb values will be captured and analyzed in the efficacy analyses.

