APPENDIX C. DOSE ADJUSTMENT GUIDELINES FOR ROXADUSTAT

All dose adjustments should be based on Hb values using a point-of-care device, such as HemoCue® or CritLine®. In the event that the central lab Hb value of the site visit is significantly different and the dose adjustment decision based on the HemoCue® / CritLine® value is being re-considered, the Medical Monitor should be contacted, if possible.

Dose adjustment reviews will occur on Week 4, and at intervals of every 4 weeks thereafter (Weeks 8, 12, 16, etc.), except in the event of excessive hematopoiesis, in which case doses may be adjusted at any time. In such cases, dose adjustment reviews are resumed at 4-week intervals. For example, if the subject's Hb increases > 2.0 g/dL from Week 1 to Week 3, the subject's dose is reduced by one dose step at Week 3. The next dose adjustment review should occur 4 weeks later at Week 7. If the dose adjustment interval falls on a non-study visit week (starting Week 4), the dose adjustment review should be performed at the next scheduled study visit if a dose adjustment was not required at the previous visit. For example, if a subject's visit is scheduled for Weeks 6 and 8, and the dose adjustment would occur at Week 7, then the dose adjustment should be evaluated at the Week 8 visit.

All subjects will be dosed orally TIW during the Treatment period. During the course of the study, the dose and the dosing frequency may be changed to optimize efficacy and tolerability based on the clinical judgment of the investigator and study medical monitor. If a subject requires < 20 mg TIW (ie, < 60 mg per week) to maintain the target Hb level, the dosing frequency should be reduced in a step-wise fashion eg, TIW to BIW, BIW to QW, QW to Q-2 Week etc. The Medical Monitor should be notified as soon as possible of such dose change. The maximum roxadustat dose is 3.0 mg/kg per dose or 400 mg (whichever is lower).

The following scenarios are defined as “excessive hematopoiesis”;

Hb increases by > 2.0 g/dL at any time within a 4 week period: reduce the dose by one dose step.

Hb reaches or exceeds 13 g/dL: hold dosing, check Hb weekly. Resume dosing when Hb < 12.0 g/dL (for US subjects central lab Hb value preferred), at a dose that is reduced by two dose steps.

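### The SAP drops three of the protocol's nine efficacy endpoints and its Hb-range table without visible notice, leaving no visible efficacy output with an upper Hb limit

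*Protocol*

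**What the plan says.** Protocol 11.2.1 and 11.3.6 both deal with out-of-range Hb. The first says "Out-of-range Hb values need not be reported as AEs as these Hb values will be captured and analyzed in the efficacy analyses". The second is firmer: "out-of-range Hb values should not be reported as AEs as these Hb values will be captured and analyzed in the efficacy analyses". It also keeps accompanying signs, symptoms or a diagnosis reportable, so only the bare laboratory value is exempt.

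The protocol plans several efficacy outputs that would show Hb above range, or the response to it. Section 3.1 lists "Number (%) of subjects maintaining Hb between 10-13 g/dL for at least 60% of scheduled Hb assessments" (counted from the first value of 10 g/dL or higher), "Number (%) of subjects with phlebotomies", and Hb variability. Section 10.6.2 adds a tabulation by 4-week interval "for a variety of Hb ranges between 11.0 and 13.0 g/dL, as well as above or below these ranges". Section 10.7 then commits the sponsor as follows: "Any significant changes to the analyses described in this protocol will be highlighted in the SAP".

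SAP 4.1 lists six efficacy endpoints: mean Hb, mean Hb of at least 10 g/dL, rescue therapy, average weekly dose, dose adjustments and oral iron dose. SAP 10.1 gives the Hb analyses for the first two. Neither section sets an upper Hb limit. SAP 1 describes the plan as a more detailed elaboration of the protocol and places the table, listing and figure specifications in a separate document.

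**The concern.** Excluding a laboratory value from adverse event reporting is reasonable if it is analysed elsewhere. Here the protocol names the efficacy analyses as that other place, and the planned analyses that would show the high side are the ones missing from the SAP. The 10-13 g/dL endpoint and the range table carry the upper limits. Phlebotomy is an intervention that protocol 4.3.2 names for excessively high Hb.

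The primary objective is long-term efficacy and safety in the maintenance of Hb. If the SAP is followed as written, that objective gets a threshold result on the low side only. A reader of the report would learn how many subjects stayed at or above 10 g/dL, but not how many stayed in range or went above it. The protocol itself treats 13 g/dL as a level that matters: "Hb reaches or exceeds 13 g/dL: hold dosing, check Hb weekly".

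**Working it through.** The documents give no power or precision figure to reproduce, because no power analysis was used. The check is a line-by-line match of protocol 3.1 against the visible SAP.

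| Protocol 3.1 endpoint | Visible SAP |
|---|---|
| Mean Hb over time | 4.1, 10.1 |
| Mean Hb of at least 10 g/dL | 4.1, 10.1 |
| Hb 10-13 g/dL for at least 60% of assessments | none |
| Rescue therapy | 4.1, 10.1 |
| Phlebotomies | none |
| Weekly dose | 4.1, 8.1 |
| Dose adjustments | 4.1, 8.1 |
| Hb variability | none |
| Withdrawal for inadequate efficacy | 6, through discontinuation reason |

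Count: 9 endpoints - 5 in SAP 4.1 - 1 plausibly covered by SAP 6 = 3 unmatched, and 3/9 = 33%. Without credit for the disposition summary the count would be 4. The 10.6.2 range table is a further unmatched item and is not among the nine.

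Next, the visible SAP outputs that could show high Hb:

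- **Efficacy (4.1, 10.1).** One Hb threshold (mean of at least 10 g/dL) and no upper threshold.
- **Descriptive statistics (5.2, 11.2).** These include quartiles and a maximum. A maximum shows that a high value occurred, not in how many subjects. The by-visit standard deviation measures spread between subjects; the protocol does not define Hb variability, so this does not clearly replace it.
- **Dose decreases and holds (8.1).** Subjects are counted, but the counts are not tied to an Hb value.
- **Clinically significant laboratory changes (4.2) and the PCS determination (13.2).** Both could include Hb, but no Hb criterion is stated. They are also not the efficacy analyses that the protocol relies on.
- **Listings (13.2).** All assessments are listed. Protocol 10.6.4 adds that "Laboratory values outside of normal limits will be identified in the subject data listings with flags for high and low values". High values can be found there by reading subject by subject.

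An illustration with assumed values shows what the retained endpoints can hide. Suppose that in one period 3 of the 15 subjects average 13.5 g/dL and 12 average 11.0 g/dL. The group mean is (3 × 13.5 + 12 × 11.0)/15 = 172.5/15 = 11.5 g/dL, and 15/15 subjects meet the threshold of at least 10 g/dL. Neither retained Hb endpoint shows the three subjects, although the maximum would show that at least one high value exists. The documents do not give the actual number of high readings, and none is estimated here.

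**The case against.** The strongest reply is that high Hb is neither hidden nor unreported. The protocol promises that values will be captured and analysed, not counted above a limit, and Hb means, quartiles and maxima do analyse them. Symptoms and diagnoses remain reportable. A subject with sustained high Hb should trigger a hold and enter the dose-hold count. Under Appendix C, failure to follow the hold can still be a protocol deviation. With 15 subjects, no control group and full listings, individual high values are recoverable. All of this stands, and it limits the consequence. It does not replace the planned in-range result or supply the missing notice.

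Several stronger readings are tempting, but the documents do not support them:

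- **That no SAP output counts subjects with high Hb.** SAP 4.2 and 13.2 might do so under criteria that are not stated, and the separate specifications were not seen. The supportable statement concerns visible efficacy outputs.
- **That a central-laboratory count at 13 g/dL is a count of protocol-defined excessive hematopoiesis.** The synopsis bases that assessment on point-of-care Hb, as Appendix C does for dose adjustment. Protocol 10.6.2 and SAP 5.2 use central values for analysis. Only the cut-off is shared.
- **That protocol 10.7 requires every omission to be justified.** It requires significant changes to be highlighted. Section 10.6.2 also sets out no specific analysis for the 10-13 g/dL endpoint or for Hb variability; only the general statement in 10.6 reaches them. Phlebotomies and the range table are the clearer departures.
- **That the items were dropped because of the data.** The SAP describes completed enrolment in an open-label study, but nothing shows when or why the items were left out.

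**Conclusion.** The point holds as a traceability and completeness gap. Three of nine protocol efficacy endpoints (33%) and one planned tabulation have no counterpart in the visible SAP, and no visible text highlights this. The visible efficacy analyses have one lower Hb threshold and no upper one, while the reason for exempting bare out-of-range values from adverse event reporting depends on those analyses. The other outputs replace what was planned only in part.

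The conclusion assumes that the disposition summary covers withdrawal for inadequate efficacy, and that neither the removed SAP front matter nor the separate specifications already address the matter. If the specifications hold a suitable table, the reporting gap closes, but the missing notice in the SAP remains. The study is descriptive, so no test or error rate is affected. What is affected is whether the report shows Hb control on both sides of the range. It should be fixed, and the fix is easy.

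**What to change.** 1. In SAP 4.1 and 10.1, restore the 10-13 g/dL endpoint, the Hb-range table, Hb variability (with a definition) and the phlebotomy count. Highlight as a change from the protocol any item that is dropped.
2. Within the range table, report the number (%) of subjects with any central-laboratory Hb of 13.0 g/dL or more, using all scheduled and unscheduled values. Label it as a central-laboratory count at the protocol's 13 g/dL cut-off, not as a count of excessive hematopoiesis.
3. State whether a value of exactly 13.0 g/dL falls inside the 10-13 range or above it, since the two limits touch.
4. If the separate specifications already contain such a table, cite it in the SAP.

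The cost is SAP wording and a few descriptive tables on 15 subjects, with the Hb results drawn from data already held. With this sample each subject moves a percentage by 1/15 = 6.7 points, so counts should be shown beside percentages. The drawback for the sponsor is that the Hb-control figures may look less favourable.
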